8.3.7 REPORTING EVENTS TO PARTICIPANTS

Adverse Event (AE) Reporting:

Any potential adverse event or a serious adverse event mentioned above will be reported during the trial. An AE will be defined as any unfavorable and/or unintended sign, symptom, or injury temporally associated with the procedure or other study medication. A serious adverse event (SAE) is defined as any untoward/undesirable adverse experience related to a study intervention/medication that results in any of the following outcomes: 1) death; 2) a life-threatening adverse experience; 3) need for additional surgery; 4) a permanent or significant disability/incapacity; 5) important medical events that may not result in death, be life-threatening, or require additional surgery.

8.3.8 EVENTS OF SPECIAL INTEREST

Not applicable.

8.3.9 REPORTING OF PREGNANCY

Not applicable

8.4 UNANTICIPATED PROBLEMS

8.4.1 DEFINITION OF UNANTICIPATED PROBLEMS (UP)

Definition of unanticipated problems: unanticipated adverse device effect, any serious adverse effect on health or safety or any life-threatening problem or death caused by, or associated with, a device, if that effect, problem, or death was not previously identified in nature, severity, or degree of incidence in the investigational plan or application (including a supplementary plan or application), or any other unanticipated serious problem associated with a device that relates to the rights, safety, or welfare of subjects.

This includes:

1. Development of carotid cavernous fistula
2. loss of vision
3. renal dysfunction due to contrast toxicity
4. seizures

An incident, experience, or outcome that meets the definition of an UP generally will warrant consideration of changes to the protocol or consent in order to protect the safety, welfare, or rights of participants or others. Other UPs may warrant corrective actions. Examples of corrective actions or changes that might need to be considered in response to an UP include:

- Modification of inclusion or exclusion criteria to mitigate the newly identified risks
- Implementation of additional safety monitoring procedures
- Suspension of enrollment of new participants or halting of study procedures for enrolled participants
- Modification of informed consent documents to include a description of newly recognized risks
- Provision of additional information about newly recognized risks to previously enrolled participants.

8.4.2 UNANTICIPATED PROBLEM REPORTING

The PI will report unanticipated problems (UPs) to the reviewing DSMB and the Institutional Review Board (IRB). The UP report will include the following information:

- Protocol identifying information: protocol title and number, PI's name, and the IRB project number;
- A detailed description of the event, incident, experience, or outcome;
- An explanation of the basis for determining that the event, incident, experience, or outcome represents an UP;
- A description of any changes to the protocol or other corrective actions that have been taken or are proposed in response to the UP.

8.4.3 REPORTING UNANTICIPATED PROBLEMS TO PARTICIPANTS

Not applicable

9 STATISTICAL CONSIDERATIONS

9.1 STATISTICAL HYPOTHESES

Primary endpoints:

Cognitive outcome at 12-month follow-up assessed mainly by a specifically designed battery of 14 cognitive tests including MoCA.

Secondary endpoints:

1. Safety: Occurrence of Stroke/TIA, Cerebral Hemorrhage, or Death

Exploratory endpoints:

1. Biomarkers: A) The presence/absence of lactate on 1H-MRI spectroscopy in centrum semiovale in the ipsilateral side of COICA; B) The change in size of amygdala and hippocampus in the ipsilateral side of

COICA; C) improved and/or normalization of MTT and/or PTT on CTP specifically in the ipsilateral MCA territory.

Subgroups: Gender difference.

9.2 SAMPLE SIZE DETERMINATION

To maximize success of the intervention, we will only enroll subjects with classification of A, B, or C. The current success rate for revascularizing types A & B using EVT is 100% and type C using the Hybrid technique is 80% making the success rate for the whole sub-cohort is 93%. Based on our preliminary data and others, the mean difference in the pre- and post-procedure MoCA score was between 5-8 points. Using two comparisons: A) comparison between intervention vs. best medical management and B) pre- and post-intervention for successful vs unsuccessful intervention. We pooled the data for these studies, and then used the lower and upper ends of the confidence interval calculated between the suggested groups for the trial (best medical management vs. intervention). Doing so, we will assume the difference between pre- and post-procedure MoCA score to be 2 points and standard deviation to be 2 points. Assuming $\alpha=0.05$; $\beta=0.8$; and power of 80%, then our total sample size needed is 34 (Table 2). Based on our previous clinical trial experiences, we anticipate maximum of 10% drop out. Given that, then total sample size needed is 38 subjects with 19 subjects in each group.

Sample size estimates: Total N						
MoCA Score	Difference in total points between pre and post procedure	1		2		3
		1	2	1	2	1
	Standard Deviation difference between pre & post procedure	1	2	1	2	1
	Power :					
0.8		34	128	5	34	6
0.85		38	146	12	38	8
0.9		46	172	14	46	8
0.95		54	210	16	54	8
						26

9.3 POPULATIONS FOR ANALYSES

Data analysis will be performed based on Intention-to-Treat (ITT).

9.4 STATISTICAL ANALYSES

9.4.1 GENERAL APPROACH

The analysis will be intention to treat.

- 1) Comparison of treatment groups of baseline variables
- 2) Comparison of primary endpoint
 - a. MoCA change
 - b. Cognitive battery summary score
- 3) Comparison of secondary endpoints
- 4) Exploratory analysis of associations of exploratory endpoints with cognitive change

9.4.2 ANALYSIS OF THE PRIMARY EFFICACY ENDPOINT(S)

Primary Endpoint: Montreal Cognitive Assessment (MoCA) and cognitive battery of tests. They will be administered by a neuropsychologist masked to treatment at the pre-treatment, at 3 month and 12 month assessments. The battery is designed to assess left hemisphere function, right hemisphere function, and global function. All tests had published age-adjusted norms

10,12,38,59,60,76,80,95,101,108. All subjects will undergo all 14 cognitive tests. The order of test administration will remain constant, accommodating the delays required for recall intervals and minimizing stimulus interference in memory tasks. The raw score for each test for each subject will be converted into test-specific z score for each test in the battery. Then a composite z score based on average z score for the tests for each subject (sum of the z scores divided by the number of tests included) will be calculated. A two-sided type I error rate of 0.05 will be used.

A linear mixed effect model (PROC MIXED in SAS, Version 9.4) will be used to compare the two groups (medical management vs. surgical intervention) with the change in MoCA as the dependent variable across the repeated measures of 6 months and 12 months. The main independent variable is the intervention. The multivariable model will be adjusted for the following covariates: age, gender, education level (\leq 8th grade, 9th–12th grade [high school], or \geq 13 years [some college]), ICA side, and pre-treatment depression (as measured by the Center for Epidemiologic Studies–Depression scale). The correlation coefficient between MoCA change and the composite cognitive score will be calculated. A second comparative model of the interventions will be performed to support the primary analysis. It will use the change in composite cognitive z score as the dependent variable. Similar analysis using mixed linear models and covariates will be done.

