We selected a battery of tests that includes a standard screening measure (the MoCA), to facilitate comparisons to other studies that have used this as the primary cognitive outcome measure. The battery includes a number of well-standardized, widely used cognitive tests that measure various aspects of cognitive and behavioral functioning, including intelligence, attention, processing speed, memory, speech and language, visuoconstruction, and executive functioning. We selected a set of tests that can be administered in a one-hour session, and that are highly efficient (providing the highest yield for time required). Also, for all of these tests we have standardized information about the effects of repeat assessment, and/or multiple forms of the tests that allow practice effects to be either obviated or measured and factored into the analyses. A general reference for the neuropsychological assessment battery we are proposing is Lezak, Howieson, Bigler, and [name] (2012)⁵³, the standard textbook on neuropsychological assessment on which one of the current co-investigators ([name]) is a co-author.

The test battery at each time point will include the following measures:

1. Montreal Cognitive Assessment (MoCA): This is a widely used screening instrument designed for the detection of cognitive impairment ⁶². Total points possible on this test range from 0 – 30.
2. Wide Range Achievement Test-5 (WRAT-5)¹⁰⁴, Word Reading subtest: This is a single-word oral reading test, well-validated as an estimate of baseline general intelligence (Wilkinson & Robertson, 2017). The number of correctly read words is converted to an age-adjusted standard score (mean = 100, standard deviation = 15).
3. Wechsler Adult Intelligence Scale – IV (WAIS-IV), Digit Span subtest: This test measures complex attention and working memory. The participant is asked to repeat a series of aurally presented digits of increasing length (a) verbatim, (b) in reverse order, and then (c) sequentially from lowest to highest ¹⁰². The total score is converted to an age-corrected scaled score (mean = 10, standard deviation = 3).
4. WAIS-IV, Coding subtest: This test measures sustained attention and processing speed. Using a key, the participant writes the symbol corresponding to its number as quickly and accurately as possible. The total score is converted to an age-corrected scaled score (mean = 10, standard deviation = 3).

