10. Boston Diagnostic Aphasia Examination, Complex Ideational Material subtest (CIM): This is an auditory comprehension test developed to measure sustained attention and receptive language skills. It consists of yes/no questions of increasing difficulty in which the participant must recall common facts, and infer details contained in short, aurally presented stories 38. The range of scores on this test is 0 – 12, and raw scores are converted to T-scores.

11. Trail-Making Test, part A (TMT-A): This test measures attention, processing speed, and visuomotor skills. Participants are asked to connect 25 numbered circles as quickly and accurately as possible 78. The score is the time to completion (in seconds), converted to a T-score.

12. Trail-Making Test, part B (TMT-B): This test measures divided attention, processing speed, cognitive flexibility, and executive function. The participant is asked to connect 25 numbered and lettered circles, alternating between the two in numerical and alphabetical order (e.g., 1, A, 2, B, 3, C, etc.). The score is the time to completion (in seconds), converted to a T-score.

13. Beck Depression Inventory-Fast Screen (BDI-FS): This is a self-report inventory of depressive symptomatology, designed for use in persons with medical illnesses6. Scores are converted to a range of depression severity (none, mild, moderate, severe).

14. Iowa Scales of Personality Change (ISPC): On this measure, a collateral of the patient (e.g., spouse, child) rates behavioral and personality characteristics of the patient before and after a particular event (for the current study, this will be the surgical intervention) 4. The ISPC measures changes in personality and behavior, and will be administered only at the post-surgery evaluations (to the collateral). Scores are converted to z-scores.

The score on the MoCA will serve as an overall proxy for cognitive outcome, and can be used to measure change (e.g., pre to post). Scores from tests 2-12 in the proposed neuropsychological battery will be converted to z-scores, to facilitate direct comparisons across the test battery for pre to post (including short- and long-term outcomes). These will also be used to analyze changes in specific cognitive domains. The score from the BDI-FS will be used as a covariate to assess the role of depressive symptomatology in cognitive performance.

Demographics collected:

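### The cognitive change composite includes WRAT-5 Word Reading, described as a baseline intelligence estimate; if that test does not respond, the supportive effect shrinks by about 7-9%

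*Combined protocol and SAP*

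**What the plan says.** Section 9.4.2 first standardises the battery: "The raw score for each test for each subject will be converted into test-specific z score for each test in the battery". It then describes the average: "Then a composite z score based on average z score for the tests for each subject", calculated as the "sum of the z scores divided by the number of tests included". It neither names the tests included nor excludes any. The same section says "All subjects will undergo all 14 cognitive tests".

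The composite feeds a second model: "A second comparative model of the interventions will be performed to support the primary analysis". Of that model it says: "It will use the change in composite cognitive z score as the dependent variable". Section 9.4.1 also lists a battery summary score, next to MoCA change, under the comparison of the primary endpoint.

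Sections 4.1 and 8.1 (Cognitive Testing) give a narrower set for pre-to-post comparison: "Scores from tests 2-12 in the proposed neuropsychological battery will be converted to z-scores". WRAT-5 Word Reading is test 2. The same sections describe it as a single-word reading test, "well-validated as an estimate of baseline general intelligence". They give the depression screen (BDI-FS) a covariate role. They give WRAT-5 no separate role, and it is not among the covariates in 9.4.2.

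**The concern.** A change composite should be built from measures that the treatment could plausibly move. By the protocol's own description, WRAT-5 estimates a baseline level. The other cognitive tests are described by a function they measure or, for the MoCA, as a screen for impairment. If WRAT-5 stays where it started in both arms, averaging it in pulls the composite treatment difference toward zero.

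What is at stake is the size, and possibly the precision, of the planned support for the MoCA result in a trial meant to inform a go/no-go decision on phase 3 (section 2.1).

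The point is separate from the non-cognitive scales. Restricting the composite to tests 2-12 removes BDI-FS and the personality-change scale (ISPC, given only after surgery), but it keeps WRAT-5. And because the tests included are left open, WRAT-5 could be kept or dropped after the results are known.

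**Working it through.** **1. The plan's own figure.** Section 9.2 assumes a MoCA difference of 2 points and SD of 2, so d = 2/2 = 1, with two-sided alpha 0.05 (section 9.4.2) and 80% power. A two-sample t-test (noncentral t) gives 78.1% power with 16 per arm and 80.7% with 17 per arm. So 17 per arm, 34 in total, is reproduced. Allowing for 10% dropout, 34/0.9 = 37.8, rounded up to 38. These figures concern the MoCA only. The plan states no effect, SD or power for the composite.

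**2. Is WRAT-5 in the composite?** Yes on both readings: each test in the battery (9.4.2) and tests 2-12 (4.1, 8.1).

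**3. Effect in z units.** Assume WRAT-5 has zero treatment effect and the other k - 1 components share effect D. The composite effect is then D(k - 1)/k, a loss of 1/k.

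| Components averaged | k | Factor | Loss |
|---|---|---|---|
| Tests 2-12 | 11 | 10/11 = 0.909 | 9.1% |
| Tests 2-12 plus MoCA | 12 | 11/12 = 0.917 | 8.3% |
| All 14 tests, or every separate score from tests 2-12 | 14 | 13/14 = 0.929 | 7.1% |

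The second way to reach 14: HVLT-R yields three scores and BVRT two, so tests 2-12 give 9 + 3 + 2 = 14 scores. The all-14-tests reading is nominal, because ISPC has no baseline from which to form a change.

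**4. Standardised effect and power.** Take m = 10 other tests. Scale each change score to SD 1, with correlation r between any two. Let WRAT-5 change have SD s and correlation w with each of the others. The sum over the ten tests has variance V0 = m + m(m - 1)r. Adding WRAT-5 gives V1 = V0 + s² + 2mws. The sum of effects is 10D either way and the divisor cancels, so the standardised effect is multiplied by √(V0/V1).

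Example: r = 0.5, s = 1, w = 0.5. V0 = 10 + 90 × 0.5 = 55 and V1 = 55 + 1 + 10 = 66. The ratio is √(55/66) = 0.913.

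The documents give none of r, s or w. The table assumes r from 0.2 to 0.5, sets d = 1 for the composite without WRAT-5 (borrowed from the MoCA for illustration), and uses 17 per arm.

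| WRAT-5 change | Ratio | Power |
|---|---|---|
| Constant (s = 0) | 1.000 | 80.7% |
| Half SD, uncorrelated (s = 0.5, w = 0) | 0.996-0.998 | 80.4-80.5% |
| Full SD, uncorrelated (s = 1, w = 0) | 0.983-0.991 | 79.3-80.0% |
| Half SD, correlated (s = 0.5, w = r) | 0.955-0.962 | 77.1-77.6% |
| Full SD, correlated (s = 1, w = r) | 0.913-0.921 | 73.3-74.0% |

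The loss from 80.7% is therefore 0 to 1.4 points if WRAT-5 change is constant or uncorrelated, 3.1 to 3.6 points at half SD with correlation, and 6.7 to 7.4 points at the extreme.

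**The case against.** The strongest objection is to the premise. The protocol nowhere says that WRAT-5 is not expected to change. It gives the test at every time point, counts intelligence among the functions the battery covers, and names tests 2-12 for pre-to-post comparison. Where it wanted a covariate role it said so, for BDI-FS. So the authors may have meant WRAT-5 as a repeated outcome. This stands: non-response is an inference from the protocol's description, and the 7-9% is conditional on it.

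A second objection also stands. A reader might take the largest power loss as the expected one. That case needs WRAT-5 change to be as variable as the other tests and equally correlated with them, which sits uneasily with a stable reference measure. If its change is constant, mean and SD shrink together and nothing is lost but scale. If its change is unrelated noise, the loss is about a point or less.

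Third, the open list of components is the wider gap, and listing them would settle WRAT-5 as well. That is true of the remedy, but adopting the protocol's own narrower list, tests 2-12, would leave WRAT-5 in, so it has to be named.

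A reader might also infer that baseline WRAT-5 should replace the three-band education covariate. Nothing in the documents shows a precision gain from that. Because 9.4.2 uses similar covariates in both models, the swap could also alter the primary MoCA model.

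**Conclusion.** The point holds as a minor one. As written, the plan averages into a change outcome a test that it describes as estimating a baseline level, whichever reading of the composite is used. If WRAT-5 does not respond and the other components share an effect, the composite effect in z units is understated by about 7-9%. Illustrative power falls by nothing to about 1 point in the cases nearest to a stable reference measure, and by about 7 points at most in the cases examined. Those power figures rest on a borrowed d = 1 and on assumed SDs and correlations.

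A reader might infer that the trial's main comparison is underpowered or biased. The documents do not support that. The MoCA change model does not use the composite, and the sample size rests on the MoCA alone. Under the stated premise the dilution works toward no difference and cannot by itself create a false positive finding. The listing of the summary score under the primary endpoint in 9.4.1 gives the composite some prominence, but 9.4.2 makes its model supportive.

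**What to change.** In section 9.4.2, list the tests, and the scores within each test, that enter the composite, and state the divisor. Say that WRAT-5 Word Reading is excluded from the change composite and reported as a baseline descriptor. Align the wording on tests 2-12 in sections 4.1 and 8.1. Keep the prespecified education covariate and the testing schedule as they are.

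The cost is wording only, since the test is already scheduled. The downside is a composite with one fewer test. If the investigators do expect WRAT-5 to respond, they should give that rationale when listing it as a component, before outcome data are seen.

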8 STUDY ASSESSMENTS AND PROCEDURES

8.1 EFFICACY ASSESSMENTS

Cognitive Testing:

Participants who are enrolled in this study will undergo a standardized neuropsychological test battery at 3 time points with the test score calculated at 12-month follow-up is considered the primary endpoint for the trial:

- (1) Baseline: prior to procedure.
- (2) Early Post-op: At 6 months post-discharge from hospital, to investigate short-term cognitive outcome;
- (3) Late Post-op: At 12 months post-discharge from hospital, to investigate long-term cognitive outcome.

We selected a battery of tests that includes a standard screening measure (the MoCA), to facilitate comparisons to other studies that have used this as the primary cognitive outcome measure. The battery includes a number of well-standardized, widely used cognitive tests that measure various aspects of cognitive and behavioral functioning, including intelligence, attention, processing speed, memory, speech and language, visuoconstruction, and executive functioning. We selected a set of tests that can be administered in a one-hour session, and that are highly efficient (providing the highest yield for time required). Also, for all of these tests we have standardized information about the effects of

repeat assessment, and/or multiple forms of the tests that allow practice effects to be either obviated or measured and factored into the analyses. A general reference for the neuropsychological assessment battery we are proposing is Lezak, Howieson, Bigler, and [name] (2012)⁵³, the standard textbook on neuropsychological assessment on which one of the current co-investigators ([name]) is a co-author.

The test battery at each time point will include the following measures:

1. Montreal Cognitive Assessment (MoCA): This is a widely used screening instrument designed for the detection of cognitive impairment ⁶². Total points possible on this test range from 0 – 30.
2. Wide Range Achievement Test-5 (WRAT-5)¹⁰⁴, Word Reading subtest: This is a single-word oral reading test, well-validated as an estimate of baseline general intelligence (Wilkinson & Robertson, 2017). The number of correctly read words is converted to an age-adjusted standard score (mean = 100, standard deviation = 15).

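### The primary MoCA model names no 12-month contrast, although the declared primary endpoint is at 12 months, and it adjusts for a depression scale the trial does not collect

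*Combined protocol and SAP*

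**What the plan says.** **Endpoint and time.** The synopsis (1.1) and Sections 3, 4.1, 8.1 and 9.1 all place the primary endpoint at 12 months. Section 8.1 says the "test score calculated at 12-month follow-up is considered the primary endpoint for the trial" and describes the earlier visit separately: "At 6 months post-discharge from hospital, to investigate short-term cognitive outcome".

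**Primary model.** Section 9.4.2 specifies a linear mixed model with "change in MoCA as the dependent variable across the repeated measures of 6 months and 12 months". It adds: "The main independent variable is the intervention". The listed covariates are age, gender, education in three levels, ICA side and "pre-treatment depression (as measured by the Center for Epidemiologic" Studies depression scale (CES-D). No visit term, interaction, covariance structure or time-specific contrast is given there or elsewhere in Section 9.

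**Depression measure.** The only depression scale in the 14-test battery is the BDI-FS (test 13). Sections 4.1 and 8.1 both say its score will be the covariate. The schedule of activities does not list the CES-D, and the baseline data list in Section 4.1 has only depression history and antidepressant use.

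**Measure.** Section 9.1 declares "Cognitive outcome at 12-month follow-up assessed mainly by a specifically designed battery of 14 cognitive tests including MoCA". Section 9.4.1 lists MoCA change and "Cognitive battery summary score" together under the primary endpoint. Section 9.4.2 gives the composite a lesser role: "A second comparative model of the interventions will be performed to support the primary analysis".

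**The concern.** A treatment main effect in a model over two visits, with no interaction, estimates one common effect across those visits. With complete data and equal variances this is the simple average of the 6- and 12-month differences. It equals the 12-month difference only if the effect is the same at both visits. An effect that fades could then support a claim on a 12-month endpoint it does not meet, and an effect that builds up could be missed.

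The trial is open label, small, and feeds a go/no-go decision on phase 3 (Section 2.1). The deciding contrast should therefore be fixed before results are seen. As written, an analyst could report either the common effect or a 12-month estimate and claim to have followed Section 9.4.2.

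Separately, the model as written cannot be fitted, because one of its covariates is not among the data collected.

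**Working it through.** **1. The plan's own figure.** Section 9.2 gives a difference of 2, SD 2, 80% power and a total of 34; Section 9.4.2 gives two-sided alpha 0.05. For a two-sample t-test with 17 per arm, the standard error is 2 × √(2/17) = 0.686, the noncentrality is 2/0.686 = 2.92, df = 32, and power is 80.7%. So 34 reproduces, and 34/0.9 = 37.8, rounded up to 38. This is an unadjusted comparison of change at one time point, and Section 9.2 does not say which visit.

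**2. Averaged test against 12-month contrast, no covariates.** Assumptions not in the documents: SD of change 2 at both visits, correlation ρ between 6- and 12-month change of 0.5 to 0.9, and the effect patterns below. The averaged effect is (d6 + d12)/2 and its SD is 2 × √((1+ρ)/2), which is 1.732, 1.844 and 1.949 for ρ = 0.5, 0.7 and 0.9. Noncentral t, df 32:

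| Effect at 6 / 12 months | Averaged effect | Averaged test rejects, ρ = 0.5 / 0.7 / 0.9 | 12-month contrast rejects |
|---|---|---|---|
| 2 / 0 | 1.0 | 37.2% / 33.5% / 30.6% | 5.0% |
| 1 / 2 | 1.5 | 68.7% / 63.3% / 58.5% | 80.7% |
| 2 / 2 | 2.0 | 90.4% / 86.6% / 82.6% | 80.7% |

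**3. Power with the listed covariates.** There are six covariate parameters (education takes two), assumed unrelated to outcome. Over simulated designs (gender 30%, education 15/45/40%, side 50%, two normal covariates; all assumed), they inflate the variance of the visit-averaged effect by V = 1.24 on average. Because they do not interact with visit, they leave the visit-difference part alone. The variance of the 12-month contrast in the two-visit model is therefore 4 × [V(1+ρ)/2 + (1−ρ)/2] × 2/17, with Satterthwaite df between 26 and 32. For an effect of 2 at both visits:

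| ρ | 12-month contrast | Averaged test | Difference (points) |
|---|---|---|---|
| 0.5 | 75% | 83% | −8 |
| 0.7 | 74% | 78% | −5 |
| 0.9 | 72% | 74% | −2 |

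Differences are from unrounded values.

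**4. Adding baseline MoCA.** Assume equal SDs and a baseline/follow-up correlation r of 0.5 to 0.9. The residual SD is 2 × √((1+r)/2), which is 1.732 at r = 0.5 and 1.949 at r = 0.9. The residual correlation between visits is (4ρ − 2(1−r)) / (2(1+r)). The 12-month contrast then has about 85-82% power at r = 0.5 and about 75-73% at r = 0.9, for ρ from 0.5 to 0.9. Against the literal averaged model without baseline MoCA, matched on ρ, the extremes are 75.4 − 83.0 = −7.6 points (r = 0.9, ρ = 0.5) and 82.3 − 73.8 = +8.5 points (r = 0.5, ρ = 0.9).

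**5. Depression covariate.** No arithmetic applies. Section 9.4.2 names the CES-D. The battery, the schedule and the baseline list do not contain it. Sections 4.1 and 8.1 name the BDI-FS score for the same role.

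**The case against.** **Averaging is not proven.** A reader might infer that the plan definitely tests the two-visit average. The documents do not support that. The full set of fixed effects is not listed, and a mixed model over two visits can deliver a 12-month estimate once the terms are added. Every endpoint statement points to 12 months. What stands is that the 12-month test is not written down.

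**The fading pattern is hypothetical.** A reader might take 37-31% as the trial's false-positive rate. It is not: it is the rejection rate of a test of a different quantity, under an assumed pattern. The only longitudinal data, Table 1 in Section 2.2, show a plateau: 24.17 − 18.18 = 5.99 points at 3 months and 24.72 − 19.1 = 5.62 at 6 months. If that holds to 12 months, averaging is the more powerful test. This stands, although Table 1 ends at 6 months and cannot settle what happens later.

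**The measure is largely settled.** Sections 4.1 and 8.1 call the MoCA the overall proxy for cognitive outcome, Section 9.2 sizes the trial on it, and Section 9.4.2 makes the composite supportive. It would be too strong to say that the deciding measure is undefined; the endpoint wording needs aligning.

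**The CES-D has an obvious replacement.** That is correct, and it is a one-phrase correction. It still has to be made, because it sits in the primary model.

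**Baseline MoCA is optional.** Agreed: it is an efficiency gain, and the test is valid without it.

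**Conclusion.** The concern holds as a specification gap in the primary analysis. The declared endpoint is at 12 months, but the model names no 12-month test. Its depression covariate is not collected, and that part needs no assumption.

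The size of the first part depends on the effect pattern. With 17 per arm, SD 2, no covariates and ρ of 0.5 to 0.9, the averaged test rejects 37-31% of the time against 5% when effects are 2 then 0. It has 69-59% power against 81% when they are 1 then 2, and 90-83% against 81% when they are equal. The correlation and the patterns are assumptions, and the choice matters only if the effect differs by visit.

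A reader might also infer that the sample size is wrong. It is not: 34 and 38 reproduce and do not change.

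**What to change.** In Section 9.4.2, specify a mixed model for MoCA change at 6 and 12 months with treatment, visit, treatment-by-visit, baseline MoCA, age, gender, education, ICA side and baseline BDI-FS score in place of the CES-D. State that the primary test is the treatment contrast at 12 months, two-sided 0.05, and that the 6-month contrast is supportive.

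State that 12-month MoCA change is the deciding measure and the composite is supportive, and align the synopsis and Sections 3, 4.1, 9.1 and 9.4.1. For the composite change score, include only tests scored at both baseline and follow-up. The ISPC is not administered at baseline; at most it has a retrospective before-event rating.

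Clerical: Section 9.4.2 mentions a 3-month assessment, but its own model uses 6 months.

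Cost: wording only. Baseline MoCA and BDI-FS are already in the battery, and N is unchanged. With the six covariate parameters, the 12-month contrast has about 72-75% power without baseline MoCA and about 73-85% with it. If the effect is constant, the contrast without baseline MoCA gives up about 2-8 points against averaging. The full proposed model runs from about 8 points lower to about 8 points higher than the literal averaged model.
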